7 STUDY ASSESSMENTS AND PROCEDURES

7.1 STUDY ASSESSMENTS

Table 1: Instrument Description

Demographics. Basic demographic information including age, gender, race/ethnicity, education level, employment status, annual income, marital status, living situation, drug allergies, and history of substance use and psychiatric disorders will be collected.

Opioid Use Questionnaire. A questionnaire assessing history of opioid use, experience of personal and observed overdoses, previous experience with naloxone, and past substance use treatment.

Decline Survey. A survey administered to participants who decline to continue with the study and receive opioid overdose and naloxone administration training to evaluate reasons for refusing training.

Pre- and Post-Training Assessment. This scale will be administered pre- and post-viewing of training materials and will assess opioid overdose and naloxone knowledge.

Follow-up Assessment. This scale includes questions about whether the participant has used their naloxone kit, who received the naloxone, who administered the naloxone, whether CPR was performed, whether a call was placed to 911, whether they have experienced personal or observed overdose, whether they have entered substance use treatment, and whether they are currently using opioids in an illicit manner.

Participant Satisfaction Survey. This assessment queries about participants' satisfaction with the online training program and postal distribution of naloxone kits (or information regarding where to obtain a kit).

7.2 ADVERSE EVENTS AND SERIOUS ADVERSE EVENTS

7.2.1 DEFINITION OF ADVERSE EVENTS (AE)

Adverse event means any untoward medical occurrence associated with the use of an intervention in humans, whether or not considered intervention-related (21 CFR 312.32 (a)).

7.2.2 DEFINITION OF SERIOUS ADVERSE EVENTS (SAE)

An adverse event (AE) is considered "serious" if, in the view of either the investigator or sponsor, it results in any of the following outcomes:

- Death
- A life-threatening adverse event (of note, the term "life-threatening" refers to an event in which the subject was at risk of death at the time of the event, rather than to an event which hypothetically might have caused death if it were more severe)

- Inpatient hospitalization or prolongation of existing hospitalization
- A persistent or significant incapacity or substantial disruption of the ability to conduct normal life functions
- A congenital anomaly/birth defect.

Important medical events that may not result in death, be life-threatening, or require hospitalization may be considered serious when, based upon appropriate medical judgment, they may jeopardize the subject and may require medical or surgical intervention to prevent one of the outcomes listed in this definition. Examples of such medical events include allergic bronchospasm requiring intensive treatment in an emergency room or at home, blood dyscrasias or convulsions that do not result in inpatient hospitalization, or the development of drug dependency or drug abuse.

7.2.3 CLASSIFICATION OF AN ADVERSE EVENT

7.2.3.1 SEVERITY OF EVENT

For adverse events (AEs), the following guidelines will be used to describe severity:

- **Mild** – Events require minimal or no treatment and do not interfere with the subject's daily activities.
- **Moderate** – Events result in a low level of inconvenience or concern with the therapeutic measures. Moderate events may cause some interference with functioning.
- **Severe** – Events interrupt a subject's usual daily activity and may require systemic drug therapy or other treatment. Severe events are usually potentially life-threatening or incapacitating. Of note, the term "severe" does not necessarily equate to "serious."

7.2.3.2 RELATIONSHIP TO STUDY INTERVENTION

All adverse events (AEs) must have their relationship to study intervention assessed by the clinician who examines and evaluates the subject based on temporal relationship and their clinical judgment. The degree of certainty about causality will be graded using the categories below. In a clinical trial, the study product must always be suspect.

- **Related** – The AE is known to occur with the study intervention, there is a reasonable possibility that the study intervention caused the AE, or there is a temporal relationship between the study intervention and event. Reasonable possibility means that there is evidence to suggest a causal relationship between the study intervention and the AE.
- **Not Related** – There is not a reasonable possibility that the administration of the study intervention caused the event, there is no temporal relationship between the study intervention and event onset, or an alternate etiology has been established.

7.2.3.3 EXPECTEDNESS

The Principal Investigator will be responsible for determining whether an adverse event (AE) is expected or unexpected. An AE will be considered unexpected if the nature, severity, or frequency of the event is not consistent with the risk information previously described for the study intervention.

7.2.4 TIME PERIOD AND FREQUENCY FOR EVENT ASSESSMENT AND FOLLOW-UP

The occurrence of an adverse event (AE) or serious adverse event (SAE) may come to the attention of study personnel during study visits and interviews of a study subject presenting for medical care, or upon review by a study monitor.

All AEs including local and systemic reactions not meeting the criteria for SAEs will be captured on the appropriate case report form (CRF). Information to be collected includes event description, time of onset, clinician's assessment of severity, relationship to study product (assessed only by those with the training and authority to make a diagnosis), and time of resolution/stabilization of the event. All AEs occurring while on study must be documented appropriately regardless of relationship. All AEs will be followed to adequate resolution.

Any medical condition that is present at the time that the subject is screened will be considered as baseline and not reported as an AE. However, if the study subject's condition deteriorates at any time during the study, it will be recorded as an AE.

Changes in the severity of an AE will be documented to allow an assessment of the duration of the event at each level of severity to be performed. AEs characterized as intermittent require documentation of onset and duration of each episode.

The Study Coordinator will record all reportable events with start dates occurring any time after informed consent is obtained until 7 (for non-serious AEs) or 30 days (for SAEs) after the last day of study participation. Events will be followed for outcome information until resolution or stabilization.

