1 PROTOCOL SUMMARY

1.1 SYNOPSIS

Title:	Increasing Naloxone Access for Persons who use Opioids: An Online Recruitment and Training Approach to Opioid Overdose Education and Naloxone Distribution
Objectives:	Feasibility and acceptability of completely remote implementation of Opioid Overdose Education and Naloxone Distribution (OEND)
Study Population:	Persons who use opioids at risk for overdose
Description of Study Intervention:	Eligible individuals who agree to participate will complete a questionnaire focused on opioid and other substance use history, overdose experiences, and history of substance use treatment. Interested and eligible individuals will then complete an online training focused on recognizing the signs of an opioid overdose, steps to take in that situation, and how to administer naloxone. Following training, participants will be randomly assigned to either receive a naloxone kit or be given information on how to obtain a kit. Online follow-up assessments will occur at one-, two-, and three-months post-training and focus on whether the participant has obtained or used their naloxone kit, naloxone kit use outcomes, and interest or engagement in substance use treatment.
Study Duration:	24 months
Subject Duration:	3 months

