Naloxone (Narcan™). With a physician's order, participants in the OEND condition will be sent a naloxone kit containing a 4mL nasal spray. Naloxone kits will be packaged in a bubble wrap envelope and sent via U.S. Postal Service. Participants in the OE alone condition will be given information on where they can obtain a naloxone kit (e.g., pharmacies with standing orders for naloxone).

Follow-up Assessments. Follow-up assessments delivered via a secure REDCap link sent to participants' email will occur at one-, two-, and three-months post-training. This assessment takes approximately 5 minutes to complete. This scale includes questions about whether the participant has used their naloxone kit, who received the naloxone, who administered the naloxone, whether CPR was performed, whether a call was placed to 911, whether they have experienced personal or observed overdose, whether they have entered substance use treatment, and whether they are currently using opioids in an illicit manner.

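### Adverse events are to be found and graded through visits and examinations that this remote trial does not have, and no systematic remote elicitation is described

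*Combined protocol and SAP*

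**What the plan says.** **Detection and grading.** Section 7.2.4 says that adverse events "may come to the attention of study personnel during study visits and interviews of a study subject presenting for medical care", or when a monitor reviews the study. It requires every event on study to be documented whatever its relationship to the intervention, on a case report form with description, onset, severity, relationship and resolution. Severity is to come from a clinician. Under 7.2.3.2, causality must be "assessed by the clinician who examines and evaluates the subject based on temporal relationship and their clinical judgment". Recording runs from consent "until 7 (for non-serious AEs) or 30 days (for SAEs) after the last day of study participation".

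**Conduct.** The synopsis (1.1) states the objective as "Feasibility and acceptability of completely remote implementation of Opioid Overdose Education and Naloxone Distribution (OEND"). Section 5.1.1 has "Follow-up assessments delivered via a secure REDCap link" at one, two and three months after training, each taking about five minutes. Sections 5.1.1 and 7.1 list the same content: whether the kit was used, who received and who gave the naloxone, CPR, a 911 call, personal or observed overdose, entry to treatment, and current illicit use. Neither the schedule of activities (1.2) nor the instrument table (7.1) has an adverse-event entry.

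**Text that points the other way.** The synopsis says that follow-up includes the outcomes of kit use, and 8.2 has an exploratory aim on kit use and its outcomes. Section 2.3.1 foresees participants describing an occasion on which they gave naloxone. Section 6.3 has staff contact a subject who misses an assessment.

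**The concern.** The safety section describes a trial with visits, patients who present for care, and a clinician who examines them. The rest of the protocol describes a trial in which the participant and the study normally meet only through an online form. If 7.2 is followed as written, its detection routes have little to work on, and the form that does reach participants is not described as asking about harms.

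Two things are at stake. First, 2.3.1 lists side effects that include seizures and death, and says that the incidence of naloxone side effects is not known. A low count obtained without systematic asking could not be interpreted in either direction. Second, other provisions depend on events being known: early termination for a serious injury or death caused by study procedures (6.1), withdrawal for an adverse event (6.2), reporting of serious events (7.2.5), and reporting of unanticipated problems, which covers risks to people other than subjects (7.3.1).

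**Working it through.** The question is mainly one of setting sections side by side. A little arithmetic fixes how many contacts are involved.

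**1. Number of follow-up forms.** Inputs: 80 participants and 20% dropout spread evenly over three months (8.2), and three follow-ups (1.2). The plan's own figure is about 70 participants on average per time point. With n(k) = 80 × (1 − 0.20 × k/3):

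- Month 1: 74.7
- Month 2: 69.3
- Month 3: 64.0
- Mean: 208/3 = 69.3, which agrees with the plan.

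Forms scheduled: 80 × 3 = 240. Forms expected after dropout: 74.7 + 69.3 + 64.0 = 208. With 1:1 allocation about 40 participants are mailed a kit. The others may obtain one, and events unrelated to kit use can occur in either group.

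**2. What section 7.2 needs and what the design supplies.**

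| Requirement | What it presupposes | What the protocol provides |
|---|---|---|
| Detection at visits or interviews (7.2.4) | Scheduled visits; subjects presenting to the study for care | No visits; emailed form at Months 1–3 |
| Detection on monitor review (7.2.4) | Something already recorded | No listed instrument that records events |
| Case report form with onset, severity, relationship and resolution (7.2.4) | A source for each field | No listed item for any of them |
| Causality (7.2.3.2) | A clinician who examines the subject | No examination; no remote assessor named |
| Severity (7.2.4) | A clinician's assessment | No route by which a clinician receives the report |
| 7- and 30-day windows (7.2.4) | Contact after participation ends | No scheduled contact after Month 3 |

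The last row takes the Month 3 form as the end of participation, in line with the three-month subject duration in 1.1.

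**3. Kinds of event against the listed items.**

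- Personal overdose: asked at each follow-up. It can be an adverse event, and a serious one if life-threatening (7.2.2).
- An emergency that led to a 911 call: asked, so some serious events could surface.
- Withdrawal symptoms, seizure or other effects in 2.3.1 after naloxone: not listed. They may be meant by kit-use outcomes, but no instrument defines those outcomes.
- Hospitalisation, a seriousness criterion in 7.2.2: not listed.
- Events unrelated to kit use, which 7.2.4 also requires: not listed, apart from overdose.
- Effects in a third party given naloxone: the form asks who received it, but no question about what followed is listed.

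**4. Staff contact.** Under 6.3, calls and letters follow a missed assessment. A participant who completes all three forms triggers none of them.

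**5. What cannot be computed.** The documents give no rate of kit use and no rate of harm. The number of events that would go unrecorded therefore has no basis in the documents, and none is offered.

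**The case against.** The strongest reply is that the documents do not show that harms will go unrecorded.

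- The routes in 7.2.4 are worded permissively and are not an exclusive list. The same section requires all events to be documented.
- The item list is introduced as what the scale includes, so it may not be complete. The questionnaire and case report form are not reproduced, and the consent form, which might tell participants how to report an event, was not available for this review.
- The synopsis, 8.2 and 2.3.1 all suggest that some account of kit-use outcomes is intended.
- The form asks about personal overdose, a foreseeable serious event in this population, at all three months.
- Staff do contact non-responders.
- Section 8 has no safety hypothesis or analysis, and 2.3.1 adds that side effects are generally mild and rare.

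Most of this stands, and it limits the claim. A reader might infer that the trial will record almost no adverse events, or that it will send a false signal of safety to the larger study. The documents support neither inference: some serious events have a route in, and the larger trial is described in 2.3.2 as evaluating recruitment, training and distribution.

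The reply does not supply a method. A duty to document events does not say how they become known, and an undefined reference to outcomes does not cover hospitalisation or events unrelated to kit use. Nothing in the reply answers who grades causality without an examination.

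**Conclusion.** The point holds as a contradiction between the safety section and the remote design, and as a gap in the described data collection. Sections 7.2.3.2 and 7.2.4 depend on visits and an examining clinician, while 1.1, 1.2, 5.1.1 and 7.1 provide neither and list no adverse-event assessment. No systematic remote elicitation is described, so harms may be missed or left ungraded, although 7.2.4 requires them all to be documented.

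In size, it concerns every scheduled follow-up form (240, or about 208 after the planned dropout) and both windows after participation. The conclusion assumes that the listed items are the substance of the form and that participation ends with the Month 3 form. If the actual questionnaire already asks about events after kit use, the gap narrows to events unrelated to kit use, grading and the windows. The feasibility and acceptability outcomes are not affected. The change is worth making because it is cheap and other safety provisions depend on it.

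**What to change.** 1. Add a short adverse-event block to each Month 1–3 REDCap form: hospitalisation or emergency visit, and any other event, with onset and resolution.
2. After reported kit use, branch to the effects listed in 2.3.1 in the person given naloxone, whether the participant or a third party.
3. Set an automatic alert to existing study staff on a positive answer.
4. Cover the 7- and 30-day windows with one automated REDCap query about 30 days after the last form, or restate the windows to match what is collected.
5. Reword 7.2.3.2 and 7.2.4 so that a named study role assesses severity and causality from the remote report, and list the block in 1.2 and 7.1.

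Cost: about 1–2 minutes on a form that now takes about 5, one extra automated email per participant, staff time for positive answers, and protocol wording that needs IRB approval.

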7.2.5 ADVERSE AND SERIOUS ADVERSE EVENT REPORTING

All serious adverse events must be reported to the IRB according to regulatory requirements. The Principal Investigator will immediately report to the sponsor any serious adverse event, whether or not considered study intervention related, including those listed in the protocol or package insert and must include an assessment of whether there is a reasonable possibility that the study intervention caused the event. Study endpoints that are serious adverse events (e.g., all-cause mortality) must be reported in accordance with the protocol unless there is evidence suggesting a causal relationship between the study intervention and the event (e.g., death from anaphylaxis). In that case, the investigator must immediately report the event to the sponsor.

All serious adverse events (SAEs) will be followed until satisfactory resolution or until the Principal Investigator deems the event to be chronic or the subject is stable. Other supporting documentation of the event may be requested and should be provided as soon as possible.

7.3 UNANTICIPATED PROBLEMS

7.3.1 DEFINITION OF UNANTICIPATED PROBLEMS (UP)

The Office for Human Research Protections (OHRP) considers unanticipated problems involving risks to subjects or others to include, in general, any incident, experience, or outcome that meets all of the following criteria:

- Unexpected in terms of nature, severity, or frequency given (a) the research procedures that are described in the protocol-related documents, such as the Institutional Review Board (IRB)-approved research protocol and informed consent document; and (b) the characteristics of the subject population being studied;
- Related or possibly related to participation in the research (“possibly related” means there is a reasonable possibility that the incident, experience, or outcome may have been caused by the procedures involved in the research); and
- Suggests that the research places subjects or others at a greater risk of harm (including physical, psychological, economic, or social harm) than was previously known or recognized.

7.3.2 UNANTICIPATED PROBLEM REPORTING

The investigator will report unanticipated problems (UPs) to the reviewing Institutional Review Board (IRB). The UP report will include the following information:

- Protocol identifying information: protocol title and number, PI’s name, and the IRB project number;
- A detailed description of the event, incident, experience, or outcome;
- An explanation of the basis for determining that the event, incident, experience, or outcome represents an UP;
- A description of any changes to the protocol or other corrective actions that have been taken or are proposed in response to the UP.

To satisfy the requirement for prompt reporting, UPs will be reported using the following timeline:

- UPs that are serious adverse events (SAEs) will be reported to the IRB within 10 working days of the investigator becoming aware of the event.
- Any other UP will be reported to the IRB within 10 working days of the investigator becoming aware of the problem.

8 STATISTICAL CONSIDERATIONS

8.1 STATISTICAL HYPOTHESES

- Primary Efficacy Endpoint(s):

Hypothesis 1 states that remote OEND will be a feasible approach and will be supported if 80 participants are recruited within the first 13 months of the study, there is an overall significant increase in opioid overdose knowledge post-training, 80% of assessment measures are completed, and 80% of participants endorse high satisfaction scores.

- Secondary Efficacy Endpoint(s):

Hypothesis 2 will be supported if there are group differences between individuals who elect to participate in overdose training and those who decline to do so such that individuals who elect to participate will be

more likely to have active opioid use, have higher severity of use, experience of past overdose, and know someone who has experienced an overdose.

Hypothesis 3 will be supported if there are group differences in kit possession and there are no relevant group differences over time (Months 1-3), as quantified by the point estimates of effect size, in behaviors such as risky opioid use and interest/seeking out treatment between participants who received a kit versus those who did not receive a kit.

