3.2 END OF STUDY DEFINITION

The study will be considered complete when at least 150 participants are recruited for the Opioid Use Questionnaire portion of the study and at least 80 participants are recruited for the training portion of the study. Participants in the training portion who have not completed a follow-up assessment will receive at least three automatic reminder emails generated by REDCap with the goal of at least 80% overall retention.

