8.2 SAMPLE SIZE DETERMINATION

We propose to recruit 80 participants to the training portion of the study over a 12-month period. Sample size was determined by feasibility, since the primary outcomes of the study are feasibility and acceptability of remote OEND. Feasibility and acceptability are operationally defined as 1) recruitment of 80 participants during the first 12 months of the project; 2) increase in opioid knowledge post-training; 3) 80% completion of assessment measures and 4) 80% endorsement of high scores on a participant satisfaction measure. An exploratory aspect of the study involves determining the occurrence of naloxone kit use and outcomes, though the study will not be powered to evaluate this and will serve as a pilot for a larger study. The fundamental purpose of the proposed pilot study is to assess feasibility and acceptability to inform future studies, not to provide sample size estimates. If testing is conducted, assuming recruitment of 80 participants with a dropout rate of 20% (consistent with prior studies), uniformly distributed over the 3-month follow-up period would result in approximately 70 participants on average at each of the three follow-up time points. The sample size provides 80% power to detect a time-averaged mean difference of .55 SD between groups for a continuous outcome, or an odds ratio of 2.69 for a binary outcome, assuming an alpha level of .05 and an intrasubject correlation of .5 (computations in PASS 11 software).

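### The primary recruitment criterion carries two deadlines, 13 months in section 8.1 and 12 months in section 8.2, with no start date for either

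*Combined protocol and SAP*

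**What the plan says.** Section 8.1 makes Hypothesis 1 depend on four conditions joined by 'and'. The first is that "80 participants are recruited within the first 13 months of the study". The others are a knowledge gain after training, 80% completion of assessments, and 80% of participants reporting high satisfaction.

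Section 8.2 states that "the primary outcomes of the study are feasibility and acceptability of remote OEND" and defines them operationally with the same four items in the same order. Its first item is "recruitment of 80 participants during the first 12 months of the project". The section opens with a plan: "We propose to recruit 80 participants to the training portion of the study over a 12-month period".

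Section 3.2 treats the study as complete when, besides a questionnaire target of 150, "at least 80 participants are recruited for the training portion of the study". It sets no month limit. The synopsis (1.1) gives a study duration of 24 months and 3 months per subject.

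There is also a small wording difference in the second criterion. Section 8.1 requires that "there is an overall significant increase in opioid overdose knowledge post-training", while section 8.2 asks only for "increase in opioid knowledge post-training".

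**The concern.** Sections 8.1 and 8.2 both set the decision rule for the primary outcome, and they give different deadlines for the same count of 80. They also use different clocks, one running from the start of the study and the other from the start of the project, and neither start is tied to an event. Award, IRB approval, first advertisement and first consent are all possible readings. A reader cannot tell whether the rules coincide or differ by a month.

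Because the four conditions are joint, missing the recruitment deadline is enough to defeat Hypothesis 1. Recruitment may continue past month 12, since section 3.2 stops on a count. An 80th enrolment in month 13 is therefore a real possibility, and the deadline or the start date could then be chosen once accrual is known.

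**Working it through.** **1. Does any other section settle the deadline?**

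- Section 3.2 gives a count with no time limit.
- The synopsis leaves at most 24 − 3 = 21 months for recruitment, which is compatible with 12 or 13.
- The opening sentence of 8.2 gives a planned duration. It agrees with the 12-month figure but sets no start date.
- No available section defines month 1 of the study or of the project.

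**2. Does the plan's power figure depend on this?** No. With 20% dropout spread evenly over three months, the numbers at follow-up are 80 × (1 − 0.2k/3) = 74.7, 69.3 and 64.0 for k = 1, 2, 3. The mean is 69.3, and the plan says about 70. With 35 per arm, three time points and correlation 0.5, the variance factor is (1 + 2 × 0.5)/3 = 0.667. The standard error is √(2 × 0.667/35) = 0.195 SD, and power at 0.55 SD (two-sided alpha .05) is Φ(0.55/0.195 − 1.96) = 80.5%, against the stated 80%. The deadline does not enter this calculation.

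**3. Required accrual.**

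- 13 months: 80/13 = 6.15 per month.
- 12 months: 80/12 = 6.67 per month, which is 8.3% faster.
- At exactly 80/13 per month, 12 × 6.154 = 73.8 participants are expected by month 12. That meets 8.1 and misses 8.2. The same holds for any constant rate from 6.15 to just under 6.67.

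**4. How often would the rules disagree?** The documents give no accrual rate, so the rates *r* below are assumptions. With constant Poisson accrual from a common start, the chance of reaching 80 by month *T* is P(Poisson(*rT*) ≥ 80). The difference between *T* = 13 and *T* = 12 is the chance that the 80th enrolment falls in month 13.

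| Rate per month | By month 12 | By month 13 | Rules disagree |
|---|---|---|---|
| 5.0 | 0.008 | 0.039 | 3% |
| 5.5 | 0.052 | 0.171 | 12% |
| 6.0 | 0.187 | 0.425 | 24% |
| 6.4 | 0.373 | 0.652 | 28% (peak) |
| 6.67 | 0.517 | 0.779 | 26% |
| 7.0 | 0.683 | 0.888 | 20% |
| 7.5 | 0.867 | 0.969 | 10% |
| 8.0 | 0.957 | 0.994 | 4% |

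The disagreement exceeds 20% only between about 5.8 and 7.0 per month. If the true rate is itself uncertain (gamma distribution, coefficient of variation 20%, also an assumption), it is 13–14% for mean rates of 6.0 to 6.67 and 11% at 5.5 and 7.5.

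**5. Knowledge wording.** Assume 80 participants and a two-sided paired t-test at .05. The smallest significant gain is 1.990/√80 = 0.223 SD of change. The chance of a positive but non-significant gain is 24% for a true gain of 0.3 SD, 6% for 0.4 SD and 0.7% for 0.5 SD. The wording matters only if the true gain is small.

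**The case against.** The best defence is that the figures can be reconciled: one month of start-up followed by 12 months of recruitment ends in month 13 of the study. This is plausible and may be what was intended. But no section mentions a start-up month, and the operational definition in 8.2 counts the first 12 months of the project, not 12 months from the opening of recruitment. The reader has to supply the reconciliation, and if it is right, one sentence would say so.

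Other objections stand in part:

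- Constant accrual is a simplification. Section 4.4 allows further online venues if recruitment is slow, and section 5.2 sets minimum shares by sex and race, so the rate could change partway through. The probabilities are illustrative. Only 6.15 and 6.67 per month come directly from the protocol.
- The disagreement figures concern the recruitment criterion alone. The overall verdict changes only if the other three criteria are also met, so they are upper bounds for a changed conclusion.
- Some front matter was not available, so the statement that no start date is defined covers the available text.
- The gap is one month in one of four criteria of a pilot whose size rests on feasibility. Reporting the date of the 80th enrolment would let any reader apply either deadline. It would not settle which rule the trial had committed to.
- The knowledge wording in 8.2 is probably shorthand for 8.1 and is a minor matter.

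**Conclusion.** The inconsistency is real and should be fixed. Two current sections give contradictory thresholds for one component of the primary outcome, and the available text does not reconcile them. The problem is a conflict in the stated rule, not missing detail.

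Its practical size depends on accrual. Near the planned pace, the choice of deadline moves the chance of meeting the recruitment criterion by about 20 to 28 percentage points; well away from that pace it hardly matters. These figures rest on assumed Poisson accrual and a common start. That an 80th enrolment in month 13 of a common clock passes one rule and fails the other rests on no accrual assumption.

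**What to change.** Before accrual data are reviewed, put the same sentence in 8.1 and in item 1 of the definition in 8.2: 80 participants recruited to the training portion within the first X months, with month 1 starting on one named calendar event. On a common clock 12 is the stricter value. If 13 was intended, correct item 1 in 8.2; if a start-up month explains the difference, say so.

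It would also help to define 'recruited' as consented, trained or randomized. Sections 3.1 and 5.1.1 place randomization after consent and training, so these dates may differ. Report the date of the 80th enrolment whichever deadline is chosen.

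As a minor alignment, carry the requirement of significance into item 2 of 8.2 and name the test, for example a two-sided paired test at alpha .05.

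The cost is a line of text and one defined date. Choosing 12 months makes the criterion harder to meet when accrual is near target: under the accrual assumptions above, 19% instead of 43% at 6.0 per month and 52% instead of 78% at 6.67. Sample size and power stay as they are.
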